## 8.2 Primary Endpoints.

**Effectiveness Outcomes.** For the outcomes described below, we only include Rx chronic medications. Though we document them, we exclude PRN, as adherence concerns are different.

**Treatment knowledge.** Patients will be asked to identify drug indication; binary classifications will be applied per drug.

**Medication adherence.** The ASK-12 Adherence Barrier Survey assesses patients' general adherence behaviors and barriers to treatment adherence. Adherence will also be measured for each Rx medication using: 1) Self-report of how many pills and how often each medicine was taken over the last 24 hours. The RC will record how many pills were taken at each time for each medicine. Correct dosing will be measured as yes/no per drug, based on having properly demonstrated dose (# pills), spacing (hours between doses), frequency (times per day), and total pills/day, 2) in-person/phone pill counts of all chronic, pill form medicines, using established guidelines employed by our team [R01HS00167; PI [name]], 3) the proportion of days covered (PDC), a measurement of days covered with medication, based on pharmacy claims. This is calculated by summing the number of days' supply obtained by a patient during a given time period and dividing by the number of days for which the medication was prescribed. For each patient, we will assess adherence within drug class. If a patient fills a prescription for a drug and switches to another drug within the same class, all prescriptions will be summed in the numerator. Adherence will be treated both continuously (PDC) and dichotomously (yes/no - PDC  $\geq 80\%$ ). Patients will be asked to sign a release at their first and/or last interview allowing us to obtain fill information from pharmacies used during the study. We will request information from pharmacies 6 months prior to baseline to a year post baseline. If the interview is completed over the phone, patients may receive a pharmacy release form by mail to sign and return to the research team. For the pill count during phone interviews, RCs will read a standardized script to ask patients to count study pills using a standardized procedure. If able, participants will be asked to join a video call so the

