**9.17 Pharmacy Release.**

To calculate PDC, we will need to collect pharmacy claims data for each patient that grants permission. For each patient, we will assess adherence within drug class. If a patient fills a prescription for a drug and switches to another drug within the same class, all prescriptions will be summed in the numerator. Once the patients have signed the informed consent, patients will be asked which pharmacies they use to fill their prescriptions. They will be asked to sign the appropriate release(s) allowing us to obtain fill information from pharmacies used during the study. We will request to obtain information for any medicine that was filled 6 months prior to baseline to 1 year post baseline. If the interview is completed over the phone, a pharmacy release form may be mailed to the participant to be filled out and returned to the study team.

★ **COVID-19 Waves 5-9 Pharmacy fill data.** For participants that complete COVID Wave 5-9, participants will be asked if they use Walgreens or CVS to fill their prescriptions. During the COVID consent process, participants will be informed that Walgreens and CVS Pharmacy may access, receive, or use their personal information, based on the pharmacies they utilize.

**9.18 Data Sources.** Data sources for this study will include in-person interviews or phone interview with participants (see attached surveys), blood pressure machine readings during in-person visits, Electronic Health Record chart review, and pharmacy data.

**9.19 Data Collection.** In order for the researchers to evaluate the intervention and how well it is being utilized, we will ask the Alliance to provide some data to Northwestern for Erie patients. For consented patients, the Alliance/Erie Family Health Center will provide data, including basic demographics, current medication lists and clinical outcomes from the patients' medical record. The Alliance/Erie Family Health Center will also provide the above detailed information in the form of de-identified, aggregate data (i.e. frequencies and means (SD) per arm) for all patients, regardless of whether or not the patient consented to participate in the study. All data will be transferred via secure Sharepoint site.

Specifically:

- Alliance will send contact information for identified eligible patients
  - Study ID
  - Patient's medical number

- Patient name
  - Clinic and provider name
  - Home and cell phone number
  - Address
  - Sex
  - Date of Birth

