  - Primary language
  - Date of last primary doctor appointment at Erie
  - All drugs prescribed (name, dose, form, GPI, instruction, date prescribed, number of refills, pharmacy, quantity)
- NU will send Alliance/Erie Family Health Center Study IDs and baseline interview dates, linked by patient ID
- Alliance will send the following information to Northwestern for consented patients:
  - Study ID
  - All values 6 months prior to baseline & 12 months post
    - Blood pressure
    - HbA1c
    - Cholesterol levels
  - Information on all prescribed medicines baseline to 12 months post (name, dose, form, GPI, instruction, date prescribed, number of refills, pharmacy, quantity)
  - Current at baseline and 12 months post
    - Chronic conditions
    - COVID-19 diagnosis and/or results of antibody test
  - All clinic visits/appointments 6 months prior to baseline and 12 months post (date, provider, meds prescribed, visit type)
  - Patient portal survey results, date completed, and possible clinic contact for patients in either of the portal arms
  - Patient portal use 6 months prior to baseline and 36 months post baseline
    - how many times patient logged on to portal
    - what portal was used for
    - when and how often portal was used

For Northwestern patients, the same data that was requested above will be obtained through an additional EDW report, including patient medications, chronic conditions, COVID-19 diagnosis and/or results of antibody test, and healthcare utilization (ED, hospitalization, primary care appointments) as well as hypertension, diabetes and cholesterol clinical values.

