Prescription medication adherence at 6 months is the primary outcome of interest for Aim 1, with treatment knowledge regimen consolidation, and clinical outcomes being relevant to hypotheses of secondary interest. We will use generalized linear mixed-effects models (GLMMs) to test for the effects of SMS text reminder and Portal, specifying the proper link functions based on the distribution of the outcome variable. Analyses will be performed using PROC GENMOD in SAS (v.9.4). SMS text reminder and Portal (both binary) and an interaction term for SMS and Portal are the three variables included in the model to denote the intervention groups and the enhanced usual care group (H1-6). Since adherence will be assessed for each medication, 2-level GLMM will be used with medications nested in participants. We will test for differences in the outcomes between each of the groups and the enhanced usual care arm to determine benefits of SMS texting or portal use, or both by constructing contrasts.

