Exploratory Analyses. In addition to the primary per-protocol analysis, we will investigate if there is a "dose response" of either intervention. Specifically, we will look at the total weeks participating in SMS text messages and the total number of portal surveys completed. Additionally, we will repeat all GLMM analyses described for Aim 1 to explore whether differences in interventions vary by relevant covariates representing patient and regimen characteristics known to impact outcomes, specifically adherence. Interaction terms will be included in models accordingly. Statistical significance for a tested interaction ( $p < 0.05$ ) will indicate that intervention groups differ in outcomes by the studied variable (i.e. age, literacy level, regimen complexity, drug class, language, activation, comfort with texting or portal, etc.). As adherence has its many measurement challenges, experts recommend triangulating with multiple measures. We will fully investigate and compare results across each adherence measure (24-hour recall, pill count, PDC) and create a general estimate of adherence via single factor score using maximum likelihood estimation. Exploratory analyses will examine HbA1c and blood pressure from baseline to 6 months, although power may be limited.

**COVID-19 Survey:** By extending each of these studies (LitCog (STU00026255), REMinD (STU00203777), COPD Multimorbidity (STU00201640), UMS Portal (STU00201639), and TAKE IT (STU00204465)) to capture an additional patient-reported outcome related to one's knowledge, attitudes and behaviors related to COVID-19, we can link participants' responses to this longitudinal survey to a minimum data set of participant characteristics that include demographic, socioeconomic, cognitive (including health literacy) and health behavioral characteristics. We will then be able to investigate determinants of COVID-19 knowledge, attitudes and behaviors without duplicating data collection efforts for these variables.

[name] will be analyzing data from the Wave 1 health literacy items.

RCs will conduct interviews by telephone using REDCap survey software. [name] (analyst) will oversee database structure & quality assurance. Participants will complete 5 phone interviews with RCs.

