Statistical analyses will be led by [name], and all analyses will be conducted with SAS 9.4 (Cary, NC). Using data from the C3 cohort, participants' perceived levels of stress has been assessed from the initial onset of the outbreak (March 13-20; C3 W1), through its rapid acceleration (March 27-April 3; C3 W2) and apex phases (May 1-22; C3 W3), and the flattening phase (July 15- August 15; C3 W4) of the COVID-19 pandemic. The additional surveys provides the opportunity to continually assess persistent stress over a span of time that likely will include the pandemic's expected, slow recovery, an anticipated second wave in the fall/winter of 2020/2021, and its eventual recovery as well. Also during this time, there may be new treatments available, as well as a vaccine for COVID-19. Initial models will examine associations between perceived stress as a result of COVID-19 and health and healthcare outcomes over time among C3 participants. As perceived stress, health and lifestyle behaviors are expected to change over time, we will use GLMMs to examine the relationship between stress, and outcomes (diet, alcohol use, smoking, physical activity, diet, weight gain, sleep, social isolation, treatment adherence, self-reported health status) using stress as a time-varying covariate. For data from the EHR, we will assess routine health care use.

11.2 **Power Considerations.** Study sample size was based on pairwise comparisons of the primary outcome of medication adherence, measured by 24-hour recall, at six months between both the SMS texting arm and the Portal arm compared to enhanced usual care (Aim1, H1-3) and the interactive effect of both SMS and Portal compared to either intervention alone (Aim1, H4-6). We expect 69% of enhanced usual care participants to be adherent at six months. Enrolling 1505 participants from 1 health center and conservatively estimating 80% retention at six months (n=1204; 172 EHR and 344 per other arms), we will have 80% power to detect a minimum absolute difference between study arms of 12% using a Type 1 error rate of 2.5%.

With the sample size set by the primary outcome of 24-hour recall at 6 months, we also show detectable effects for pill count and regimen consolidation, and for all

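### The measure called proportion of days covered is defined as an uncapped supply ratio, so it can exceed 100% and can put patients on the wrong side of the 80% cut-off in either direction

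*Combined protocol and SAP*

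**What the plan says.** Section 8.2 (Primary Endpoints, Medication adherence) lists three per-drug measures: 24-hour self-report, pill counts, and "the proportion of days covered (PDC), a measurement of days covered with medication, based on pharmacy claims". The derivation follows at once: sum the days' "supply obtained by a patient during a given time period and dividing by the number of days for which the medication was prescribed". The result is to be used both as a continuous value and as yes/no at 80% or more.

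Sections 8.2 and 9.17 assess adherence within drug class. Both say that if a patient fills one drug and "switches to another drug within the same class, all prescriptions will be summed in the numerator".

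On timing, section 9.17 requests records for any medicine "filled 6 months prior to baseline to 1 year post baseline". Section 9.19 requests "Information on all prescribed medicines baseline to 12 months post", with date prescribed, quantity and refills among the fields. Section 11.1 states that "Prescription medication adherence at 6 months is the primary outcome of interest for Aim 1", without naming the measure. Section 11.2 bases the sample size on the "primary outcome of medication adherence, measured by 24-hour recall, at six months". The exploratory analyses in section 11.1 compare recall, pill count and PDC, and "create a general estimate of adherence via single factor score using maximum likelihood estimation".

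No section caps the value, removes overlapping supply, truncates supply that runs past the end of the period, or credits supply on hand when the period opens.

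**The concern.** The name and the formula describe different quantities. Days covered is a count of distinct days on which the patient had medication. The formula adds up what was dispensed, whenever it was dispensed and however much overlaps. Four things follow from applying it literally:

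- The value can exceed 100%, so it is not a proportion.
- A fill late in the period counts in full, although most of its supply falls after the period ends.
- When a patient switches within a class before the first drug runs out, the overlapping days count twice.
- A fill obtained just before the period counts as nothing, although the patient is living on it.

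The first three push the value up and the last pushes it down. Because the value is dichotomised at 80%, these errors become wrong adherence calls. They would then enter the comparison across measures and the factor score. Leaving the period open adds an analyst's choice that should be made in advance.

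**Working it through.** The plan reports no PDC value, so there is no figure to reproduce. The check applies the written formula and a day-level count to the same fill histories.

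**Inputs from the plan:** the formula, the switching rule and the 80% cut-off (8.2, 9.17); outcome at 6 months (11.1); fills available from 6 months before to 12 months after baseline (9.17).

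**Assumptions:** a window of days 0 to 179 (180 days); drug prescribed throughout, so the denominator is 180; fills of 90 days unless stated. The fill dates are illustrations.

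**Written formula:** sum of days' supply for fills dated in days 0 to 179, divided by 180.

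**Day-level coverage:** distinct days in 0 to 179 with supply on hand, divided by 180. Early refills of the same drug are shifted forward, overlap after a switch is counted once, earlier supply is carried in, and supply is truncated at day 180.

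| Fill days | Formula | Coverage |
|---|---|---|
| 0, 150 | 180/180 = 100% | (90 + 30)/180 = 67% |
| 0, then within-class switch on day 30 | 180/180 = 100% | 120/180 = 67% |
| 0, 80, 160 | 270/180 = 150% | 180/180 = 100% |
| -10, 80 | 90/180 = 50% | 170/180 = 94% |
| 0, then switch at run-out on day 90 | 180/180 = 100% | 180/180 = 100% |
| 30-day fills on 0, 30, 120, 150 | 120/180 = 67% | 120/180 = 67% |
| -45, 45, 135 | 180/180 = 100% | 180/180 = 100% |

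The first two rows are wrongly called adherent and the fourth wrongly called non-adherent. The third row is out of range, but its yes/no call is right. The last three rows agree, so switches at run-out and plain gaps without overrun cause no error.

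**Regular refilling, no switch and no early refill.** With 90-day fills the formula can only return multiples of 90/180 = 50%. The 80% rule therefore asks only whether two fills fell inside the window.

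- Every 105 days (15-day gaps): the window holds 15 to 30 uncovered days, so coverage is 150/180 = 83% to 165/180 = 92%, always adherent. The formula gives 50% in 30 of the 105 possible alignments with baseline and 100% in the other 75. Mean: (30 × 50% + 75 × 100%)/105 = 86%, equal to mean coverage.
- Every 130 days (40-day gaps): 40 to 80 uncovered days, so coverage is 100/180 = 56% to 140/180 = 78%, never adherent. The formula gives 100% in 50 of 130 alignments and 50% in 80. Mean: (50 × 100% + 80 × 50%)/130 = 69%, again equal to mean coverage.

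The error is thus in individual values and their classification. It is not a demonstrated shift in the mean.

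**Open window.** Fills on days 0 and 90 only score 180/180 = 100% over 180 days and 180/365 = 49% over 365.

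**Second check, 182-day window (days 1 to 182).** Fills on days 1 and 170: 180/182 = 98.9% against (90 + 13)/182 = 56.6%. Fills on days -10 and 80: 90/182 = 49.5% against 169/182 = 92.9%.

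**Illustrative simulation.** It assumed 30- or 90-day fills, mean refill lateness of 0 to 30% of the supply length, and a random first-fill date. Ratios above 100% occurred in 2% to 36% of cases. Upward misclassification was 4% to 16%. Downward misclassification was 1% to 2% with 30-day fills and 11% to 19% with 90-day fills. These rates depend on the assumptions and are not estimates for this trial.

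**The case against.** The strongest reply has three parts.

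First, the downward error depends on how the period is read. If it opens on a fill and nothing is carried in, the ratio can never fall below true coverage, and error is upward only. That is correct, and it is why the claim is that the measure can err in either direction. Downward error needs a period that does not open on a fill, together with the literal reading that only supply obtained inside it counts. A window fixed to the baseline interview will commonly meet the first condition, and the second is what the sentence says.

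Second, the formula may be loose shorthand, with analysts expected to apply ordinary PDC. That is possible. But summation is stated as the method and repeated for switches in two sections, so an analyst who follows the text computes the ratio.

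Third, the reach is limited. Section 11.2 sizes the trial on 24-hour recall, and the only analysis in section 11 that names PDC is exploratory. This stands and bounds the importance of the point. It does not remove it: PDC is listed under Primary Endpoints, and section 11.1 does not say which adherence measure the Aim 1 outcome uses. It also stands that the fill histories above are constructed, so they show what can happen and not how often.

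**Conclusion.** The concern holds. As written, section 8.2 defines an uncapped possession ratio under the name of days covered. Under the stated assumptions it can reach 150%, call 67% coverage adherent, and call 94% coverage non-adherent. With regular 90-day refills, alignment with baseline alone produces a wrong call in 30 of 105 alignments (105-day interval) or 50 of 130 (130-day interval). The upward errors follow directly from the formula and switching rule. The downward errors require supply carried in and not credited. How often either occurs in this trial, and whether the arms would differ, cannot be worked out from the documents. Power is unaffected. This should be corrected before PDC is derived, but it does not undermine the recall-based comparison on which the trial was sized.

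**What to change.** In sections 8.2 and 9.17:

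- Fix the window as baseline to 6 months, matching the Aim 1 outcome. If a longer window is also wanted, name it as a separate measure.
- Define PDC per drug class as distinct days with the prescribed class medication on hand, divided by the days in the window for which the class was prescribed. That denominator runs from the later of baseline or first prescription to the earlier of 6 months or documented discontinuation.
- Shift early refills of the same drug forward, count overlapping days after a switch once, truncate supply at the end of the window, and credit carry-in from the pre-baseline fills.
- For two drugs of one class prescribed together, which the text does not address, compute coverage per drug and do not pool supply. This fits the model in section 11.1, which nests medications in participants. State how a switch is told apart from concurrent use.

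The value is then at most 100%. Keeping days prescribed as the denominator avoids penalising late starts: a drug first prescribed on day 90 and filled perfectly scores 90/90 = 100%, not 90/180 = 50%.

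The cost is wording in two sections and a short change to the derivation program. The fill records and prescribing dates are already requested. Discontinuation dates are not listed explicitly in section 9.19, but the present denominator already needs them, so their source should be named either way. PDC values may move up or down relative to the current formula.

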### **Shifting Upstream: Implementing the UMS at Prescribing vs. Dispensing Medication.**

The above AHRQ/NIH-funded trials revealed several obstacles: 1) over half of patients routinely use multiple pharmacies resulting in their continued receipt of variable Rx label instructions; 2) imparting the UMS only on drug labels was not a sufficient signal to patients to consolidate multi-drug regimens; 3) patients need comprehensive views of the UMS applied to their entire Rx regimen vs. individual Rx labels only; 4) additional reminders may be beneficial to reinforce UMS prescribing after medical encounters, helping patients remember and simplify daily Rx use, and support adherence; 5) the UMS

alone may be insufficient at addressing multifaceted concerns that may warrant more intensive counseling and monitoring (issues with costs, side effects, regimen fatigue, motivation, etc.). Both the pharmacy and patients also expressed a need for improved, plain language Rx information that provides general knowledge to support safe Rx use. Our proposal is based on evidence from the field, extensive experience with EHRs, mobile technology, patient portals, and funded development work [R18HS17220, R21CA132771, R01NR011300, R01NR012745, U19HS021093]. We will shift the implementation of the UMS to primary care, leveraging technologies that are becoming increasingly prevalent per federal mandates (Health Information Technology for Economic and Clinical Health (HITECH) Act), particularly among community health centers. We respond to the Office of the National Coordinator (ONC) ‘Meaningful Use’ criteria by leveraging an EHR to deliver standard, patient-centered information supporting safe Rx use, as well as by extending the utility of a patient web-based portal.

**Leveraging Increasingly Available Technologies to Support Medication Use.** There are increasingly available technological solutions that can be leveraged to help patients learn how to safely and appropriately take prescribed medications at a cost that is not prohibitive, including electronic health records (EHRs) with corresponding ‘patient portals’ and cell phone applications (SMS text messaging).

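### The PDC formula counts fills at pharmacies the study cannot see as uncovered days, because only its numerator is limited to captured pharmacies

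*Combined protocol and SAP*

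**What the plan says.** Section 8.2 lists PDC as the third per-drug adherence measure. It describes PDC as "a measurement of days covered with medication, based on pharmacy claims" and forms it by adding up the supply obtained and "dividing by the number of days for which the medication was prescribed". The calculation is within drug class, with switches inside a class summed in the numerator. The result is used both as a continuous measure and at an 80% cut-off.

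Access to fills depends on the patient. Section 9.17 says that for PDC "we will need to collect pharmacy claims data for each patient that grants permission". Patients are asked at consent which pharmacies they use, and then: "They will be asked to sign the appropriate release(s) allowing us to obtain fill information from pharmacies used during the study". Section 8.2 places the release at the first interview, the last, or both. After a phone interview the form may be mailed, and it must then come back. Fills are requested from 6 months before baseline to 1 year after it.

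Three other places bear on the point:

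- Section 2.2 (Shifting Upstream) lists among the obstacles met in the team's earlier trials that "over half of patients routinely use multiple pharmacies".
- Section 9.19 obtains prescription records that carry "date prescribed, number of refills, pharmacy, quantity".
- For COVID-19 waves 5-9, section 9.17 says "participants will be asked if they use Walgreens or CVS to fill their prescriptions".

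No section says how PDC is computed when some of a patient's pharmacies are not captured.

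**The concern.** The two halves of the ratio cover different sets of fills. The numerator can hold only supply dispensed at captured pharmacies. The denominator runs over all prescribed days, with no condition on where the drug was dispensed. A patient who has released one of two pharmacies stays in the PDC analysis, and supply from the other pharmacy reads as a gap.

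Section 11.1 models adherence per medication, with medications nested in participants, so each falsely low drug would enter as an observed value. Section 11.1 also plans to compare 24-hour recall, pill count and PDC and to combine them in one factor score. Capture error in PDC would pass into both.

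**Working it through.** **1. The plan's own figure.** Section 11.2 gives 80% power for a 12-point difference, 69% in enhanced usual care, 172 versus 344 evaluable patients and a type 1 error of 2.5%. The sample sizes are exact: 1505 × 0.80 = 1204 and 1505/7 × 0.80 = 172. A two-sided test of 69% against 81% gives 78.1% power, with a minimum detectable difference of 12.25 points at 80% power. A one-sided test gives 85.2%. The stated figure therefore reproduces approximately. It is for 24-hour recall. The documents give no power, capture rate or missing-data figure for PDC.

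**2. Effect within one patient or drug.** Let u be the share of days' supply dispensed at unseen pharmacies. The documents do not give u, so it is an assumption.

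Observed PDC = true PDC × (1 − u)

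| True PDC | u = 10% | u = 20% | u = 30% | Largest u that still reads ≥ 0.80 (1 − 0.80/true PDC) |
|---|---|---|---|---|
| 1.00 | 0.90 | 0.80 | 0.70 | 20% |
| 0.95 | 0.855 | 0.76 | 0.665 | 15.8% |
| 0.90 | 0.81 | 0.72 | 0.63 | 11.1% |
| 0.85 | 0.765 | 0.68 | 0.595 | 5.9% |

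A drug filled wholly at an unseen pharmacy (u = 100%) has PDC 0 if its prescribed days are counted.

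**3. Effect on an arm contrast (illustration only).** Borrow 69% versus 81% as the true proportions with PDC ≥ 80%. Take one record per patient, and suppose a share m of records, equal in all arms and unrelated to adherence, is filled wholly at unseen pharmacies. The borrowed proportions and m are assumptions.

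- Unseen counted as non-adherent: the proportions become 0.69(1 − m) and 0.81(1 − m), so the difference is 0.12(1 − m).
- Unseen set to missing: the difference stays 0.12 and the sample sizes shrink by (1 − m).

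| m | Difference, counted as non-adherent | Power | Difference, set to missing | Power |
|---|---|---|---|---|
| 0 | 12.0 points | 78% | 12.0 points | 78% |
| 10% | 10.8 points | 60% | 12.0 points | 73% |
| 20% | 9.6 points | 45% | 12.0 points | 68% |
| 30% | 8.4 points | 33% | 12.0 points | 62% |

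Under these assumptions, setting unseen records to missing costs less power than scoring them as non-adherent, and it leaves the difference undistorted.

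**4. Does it depend on where prescribed days come from?** Section 8.2 names no source.

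- If they come from the EHR prescriptions in 9.19, a drug filled wholly elsewhere keeps its denominator and scores 0.
- If they come from pharmacy records, that drug has no denominator and drops out. A drug that moves from a captured to an unseen pharmacy could still show a false gap: true PDC 1.00 with a move halfway through reads 0.50.

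The source changes how large the problem is. It does not remove it.

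**The case against.** The case against has force on several points.

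- **Source of the denominator.** The EHR is an inference from 9.19. This stands, and it is why the fix starts by naming the source.
- **Safeguards.** Section 9.17 asks about all pharmacies, without restriction to a chain, and 8.2 allows a second opportunity for releases at the last interview. Patients who grant no permission would most naturally have no PDC. This stands. A reader might infer that patients without any release score 0, but the text does not support that. The point is confined to partial capture.
- **The multiple-pharmacy figure.** It comes from earlier trials in low-income patients at community health centers in the Washington D.C. area, supplied by a central-fill pharmacy. The present sites are in Chicago. Using several pharmacies is also not the same as leaving one unreleased. So the figure shows that partial capture is foreseeable, and it does not give a rate.
- **Importance.** The sample size rests on 24-hour recall, and PDC is one of three per-drug measures that are to be compared. The stated power is untouched.
- **The 12-month request.** It does not set the endpoint, because 11.1 fixes the adherence outcome at 6 months. Pharmacies first used after the last interview matter only if the PDC window runs past it.
- **COVID-19 waves 5-9.** A reader might infer that anyone who fills outside Walgreens and CVS is scored as PDC 0. No PDC formula is given for those waves, and the question asked would itself identify non-users. That follow-up is also separate from the randomized 6-month comparison.

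What survives all of this is a stated formula with a restricted numerator, an unrestricted denominator and no rule for partial capture.

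**Conclusion.** The concern holds for patients whose pharmacies are only partly captured. As written, the formula counts their unseen fills as uncovered days, which lowers continuous PDC and moves patients below the 80% cut-off. A true 0.95 reads as 0.76 when 20% of supply is unseen, and the cut-off is crossed once more than 5.9% to 20% is unseen, for true PDC from 0.85 to 1.00. These shares are assumptions. The documents give no capture rate, so the loss over the cohort cannot be stated.

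Releases are sought in all arms, so the expected effect is dilution. A reader might infer bias between arms. That would need capture to differ by arm, and nothing in the documents shows that it does. The primary analysis is per-protocol by engagement (11.1), however, and engaged patients could plausibly return more releases, so capture should be reported by those groups too.

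This should be corrected before PDC is derived. It does not affect the 24-hour recall measure or the stated power.

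**What to change.** In sections 8.2 and 9.17:

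1. State the source of the prescribed days.
2. Count in the denominator only drug-days assigned to a pharmacy that returned fill data. Make the assignment from the pharmacy field in the 9.19 prescription data together with the pharmacies the patient named.
3. Set PDC to missing, not 0, for a drug whose pharmacy was not captured.
4. End the trial PDC window at the 6-month interview, to match the 6-month outcome in 11.1.
5. Report capture by randomized arm and by per-protocol group.
6. Add a sensitivity analysis restricted to patients whose named pharmacies all returned data, because the pharmacy on the EHR prescription may not be where the drug was filled.
7. If PDC is derived for COVID-19 waves 5-9, apply the same capture rule to fills outside Walgreens and CVS.

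The cost is a short derivation rule and a merge on a field already collected. Some drug-level PDC values become missing, possibly more than a few, with the loss of precision shown in the working.
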